3.2.1.2.2 Nighttime cough frequency

Nighttime cough frequency will be intended as the average while the subject is flagged as being asleep.

Nighttime (i.e., asleep) cough frequency is derived as the number of coughs counted during sleeping time, divided by duration of sleep time, rounded to the nearest 2 decimal places.

Nighttime (i.e., asleep) cough frequency per hour will be directly provided by Vitalograph® in the data transfer; this will be available in FA dataset under variable FAORRES when FATEST = 'Sleep Average Hourly Cough'.

The Vitalograph[®] data transfer will hold the asleep cough frequency average per hour based on the following calculation, rounded to two decimal places:

Nighttime cough frequency = ((total cough events for a session within Sleep event period) / (recording length in seconds within Sleep event period)) x 3600.

Of note: will be blank in the vendor file if the session is rejected.

For nighttime cough frequency endpoint, a natural log transformation will be applied as described for daytime cough frequency in section 3.2.1.1.

3.2.1.2.3 EXACT 14-item e-Diary Tool

A copy of the daily diary tool EXACT version 1.1 is provided in Protocol Appendix 1.

The EXACT is a 14-item Patient Reported Outcome (PRO) daily diary tool that was originally developed to quantify and measure exacerbations of COPD. Subjects will complete the EXACT scale via the study specific e-diary. E-diary tool will be completed each evening by the subject prior to bedtime, throughout study baseline to Period 2 Day 22 or premature discontinuation.

A higher score indicates a more severe condition.

Questionnaire is recorded daily, the record collected on the Day 22 visit date will be used as the post baseline value in the summary tables; if a record is not available on the exact date then the last assessment prior to the Day 22 visit date, within a window of 5 days prior to the visit date, will be used. Study baseline value will be the last assessment available prior to the first IMP intake (as defined in this SAP at section 4.2.3).

3.2.1.2.4 E-RS diary

The E-RS daily diary is a derivative instrument of the EXACT consisting of the 11 respiratory symptoms items contained within the 14-item EXACT that measures the effect of treatment on the severity of respiratory symptoms. The E-RS is not administered separately from the EXACT, both a total 14-item EXACT total score will be computed as a secondary efficacy endpoint and a separate analysis of the E-RS 11-items will be done based on the methodology reported in Bacci et al (2018). Bacci et al concluded that analyzing the E-RS daily diary instrument into four separate respiratory symptom domain scales (with no total E-RS score computed) is a valid, reliable and sensitive measure of four distinct respiratory symptoms.

The four domain scales are:

- breathlessness (E-RS items 7, 8, 9, 10, and 11; score range, 0-17)
- cough (E-RS item 2; score range 0-4)
- sputum (E-RS items 3 and 4; score range, 0-8)
- chest symptoms (E-RS items 1, 5, and 6; score range 0-12).

A higher score on the scale indicates a more severe grade to the symptom.

The cough and breathlessness symptom domain scale scores will each be studied as secondary efficacy endpoints.

Questionnaire is recorded daily, the E-RS breathlessness and cough items record collected on the Day 22 visit date will be used as the post baseline value in the summary tables; if a record is not available on the exact date then the last assessment prior to the Day 22 visit date, within a window of 5 days prior to the visit date, will be used. Study baseline value will be the last assessment available prior to the first IMP intake (as defined in this SAP at section 4.2.3).

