- Provide packing and shipping materials for return of cough monitor to Vitalograph® after removal
- Dispense investigational product as per IVRS/IWRS
- Provide subject with dosing instructions
- Dispense Subject Medication and Symptom Log
- Record and assess adverse events, concomitant medications, and therapies (including restricted and prohibited medications)

Telephone Visit 7 and 8 (Day 8 and 15)

Visit 7 and 8 (Day 8 and 18) will be performed via a telephone call to subjects. During these visits, subjects will undergo the following assessments:

- Contraceptive counseling (if applicable)
- Cough Severity Numerical Rating Scale
- Review e-diary entries with subject for compliance, and re-train on use of e-diary if needed
- EXACT version 1.1 e-diary tool and reminder to complete it daily until the next visit

- Review Subject Medication and Symptom Log with subject
- Review investigational product accountability/compliance with subject
- Record and assess adverse events, concomitant medications, and therapies (including restricted and prohibited medications)

Treatment Visit 9 (Day 21)

During this visit, subjects will undergo the following assessments:

- Spirometry
- Clinical laboratory testing (chemistry, hematology, urinalysis, and coagulation)
- PK blood sampling
- Contraceptive counseling (if applicable)
- Cough Severity Numerical Rating Scale
- Fatigue Scale (Short Form 7a)
- CGI-C
- Review e-diary entries for compliance, and re-train on use of e-diary if needed
- EXACT version 1.1 e-diary tool and reminder to complete it daily until end of treatment
- Dispense cough monitor, train subject on use and provide instruction for removing the device prior to bedtime the next day (Day 22)
- Provide packing and shipping materials for return of cough monitor to Vitalograph® after removal
- Review and re-dispense Subject Medication and Symptom Log
- Collect investigational product blister card, assess accountability/compliance and return investigational product blister card to subject
- Reminder to take the final dose of investigational product on the morning of the next day (Day 22)
- Instructions for completing the SOWS daily by e-diary for 14 days (beginning Day 23).
- Record and assess adverse events, concomitant medications, and therapies (including restricted and prohibited medications)

Follow-up Visit 10 (Day 36)

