2.2 Secondary Objective(s)

- To evaluate the effect of NAL ER tablets on the mean relative change from baseline in 24hour (combined daytime and nighttime) cough frequency (coughs per hour) at Day 22 (dose: 162 mg BID).
- To evaluate the effect of NAL ER tablets on the mean relative change from baseline in nighttime cough frequency (coughs per hour) at Day 22 (dose: 162 mg BID).
- To evaluate the effect of escalating doses of NAL ER tablets on the mean change from baseline on the Evaluating Respiratory Symptoms (E-RS[™]) diary cough scale (E-RS diary question number 2) by treatment at Days 9, 16, and 22.
- To evaluate the effect of escalating doses of NAL ER tablets on the mean change from baseline in the Cough Severity Numerical Rating Scale by treatment at Days 8, 15, and 21.
- To evaluate the effect of escalating doses of NAL ER tablets on the mean change from baseline in the E-RS diary breathlessness scale (E-RS diary questions 7, 8, 9, 10, and 11) by treatment at Days 9, 16, and 22.
- To evaluate the effect of escalating doses of NAL ER tablets on the mean change from baseline in the 14-item the EXAcerbation of Chronic pulmonary disease Tool (EXACT[®]) version 1.1 e-diary tool total score by treatment at Days 9, 16, and 22.

- To evaluate the effect of escalating doses of NAL ER tablets on the mean change from baseline in the Patient Reported Outcomes Measurement Information System (PROMIS[®]) Item Bank v1.0 Fatigue Short Form 7a scale by treatment at Day 21.
- To evaluate the change in the Clinical Global Impression of Change (CGI-C) over time by treatment measured at Day 21.

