3.2 Endpoints and Associated Variables

Primary Efficacy Endpoint

• Mean change in daytime cough frequency (coughs per hour) from baseline as assessed by objective digital cough monitoring at Day 22 by treatment. Daytime is defined as the time the subject is awake in the 24 hours after the digital cough monitor is applied for use.

Secondary Efficacy Endpoints

- Relative change in daytime cough frequency (coughs per hour) from baseline at Day 22 (dose: 162 mg BID) by treatment.
- Relative change in 24-hour (combined daytime and nighttime) cough frequency (coughs per hour) from baseline at Day 22 (dose: 162 mg BID) by treatment.
- Relative change in nighttime cough frequency (coughs per hour) from baseline at Day 22 (dose: 162 mg BID) by treatment.
- Mean change in the E-RS diary cough subscale (E-RS diary question number 2) from baseline, at Days 9, 16, and 22 by treatment.
- Mean change in the Cough Severity Numerical Rating Scale at Days 8, 15, and 21 by treatment.
- Mean change in the E-RS diary breathlessness subscale (E-RS diary questions 7, 8, 9, 10, and 11) from baseline at Days 9, 16, and 22 by treatment.
- Mean change in the 14-item EXACT v1.1 e-diary tool total score from baseline at Days 9, 16, and 22 by treatment.
- Mean change in the PROMIS Item Bank v1.0 Fatigue Short Form 7a scale from baseline at Day 21 by treatment.
- Mean change in the CGI-C over time measured at Day 21 by treatment.

| Trevi Therapeutics, Inc. | |
|--------------------------|---------------------------|
| TR12 | Statistical Analysis Plan |
| Safety | |

Safety will be assessed based on adverse events, clinical laboratory measurements, central cardiac core laboratory read ECGs, vital signs, spirometry and physical examinations.

Subjects will also complete the Subjective Opiate Withdrawal Scale (SOWS) on a daily basis via e-diary for 14 days following the last dose of investigational product, whenever that occurs and regardless of the reason (unless consent is withdrawn).

An independent Data Safety Monitoring Board (DSMB) will periodically review safety data.

Pharmacokinetics

Nalbuphine (and/or metabolites) plasma concentration will be measured.

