3.2.1.2.5 Cough Severity Numerical Rating Scale

The Cough Severity Numerical Rating Scale instrument (Boulet et al 2015) is a single-dimension 11-point Likert scale ranging from zero ("no cough") to 10 ("worst possible cough").

A copy of the Cough Severity Numerical Rating Scale is provided in Protocol Appendix 2.

The scale will be administered on paper during the Screening Visit. Once a subject is randomized, the scale will be administered via the study specific e-diary in treatment period 1 at Visit 2 (Study baseline), Visit 3 (day 8), Visit 4 (day 15) and Visit 5 (day 21), in treatment period 2 at Visit 6(Baseline), Visit 7 (day 8), Visit 8 (day 15) and Visit 9 (day 21) and at premature discontinuation visit.

Questionnaire is recorded daily, the record collected on the Day 22 visit date will be used as the post baseline value in the summary tables; if a record is not available on the exact date then the last assessment prior to the Day 22 visit date, within a window of 5 days prior to the visit date, will be used. Study baseline value will be the last assessment available prior to the first IMP intake (as defined in this SAP at section 4.2.3).

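### The SAP gives EXACT and E-RS a single post-baseline record (Day 22), contradicting its own Day 9 and 16 endpoints and by-visit summaries; the same sentence contradicts the cough NRS schedule

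*SAP*

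**What the plan says.** **Objectives and endpoints.** SAP 2.2 sets secondary objectives on escalating doses, for example the E-RS "diary cough scale (E-RS diary question number 2) by treatment at Days 9, 16, and 22". SAP 3.2 lists the matching endpoints: E-RS cough "from baseline, at Days 9, 16, and 22 by treatment", E-RS breathlessness on the same days, and "Mean change in the 14-item EXACT v1.1 e-diary tool total score from baseline at Days 9, 16, and 22 by treatment". The cough NRS is listed for Days 8, 15 and 21. Protocol 5.2 and 8.1.2 give the same days.

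**Record rule.** SAP 3.2.1.2.3 (EXACT) says that "the record collected on the Day 22 visit date will be used as the post baseline value in the summary tables". If that record is missing, the last earlier assessment "within a window of 5 days prior to the visit date, will be used". SAP 3.2.1.2.4 has the same rule for the E-RS breathlessness and cough items: the "record collected on the Day 22 visit date will be used as the post baseline value in the summary tables". SAP 3.2.1.2.5 uses it again for the NRS: "Questionnaire is recorded daily, the record collected on the Day 22 visit date" and so on, directly after listing the NRS at Visits 3 and 7 (Day 8), 4 and 8 (Day 15) and 5 and 9 (Day 21).

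**Planned summaries.** SAP 4.11.3.3 (EXACT), 4.11.3.4 (E-RS breathlessness) and 4.11.3.5 (NRS) plan summaries by treatment received and by visit. The first two add a t-test on change from study baseline. In 4.11.3.4 the cough item is flagged in a listing, but only breathlessness is named for the summary and the test.

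**Visit 8.** Protocol 6.3.2 says "Visit 7 and 8 (Day 8 and 18) will be performed via a telephone call to subjects", under a heading that gives Days 8 and 15.

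**The concern.** The variable definitions speak of one post-baseline value, while the endpoints need three per period and the analysis sections imply several. A programmer who follows the definitions produces Day 22 only. One who follows the by-visit wording has to decide which diary entry stands for Day 9 or Day 16, and nothing in the SAP says which.

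At stake are the escalating-dose objectives. Read literally, the rule yields values only at the 162 mg step, so it cannot show what happened at 54 or 108 mg BID, although the diary is completed every evening and the data exist. The t-tests in 4.11.3.3 and 4.11.3.4 name no day either, so the choice of record also decides what is tested.

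**Working it through.** The plan gives no figure to reproduce. The check is a day count, then a comparison of sections.

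**Step 1: days the rule can reach.** The record is Day 22, with a look-back of 5 days: 22 − 5 = 17. The rule covers Days 17 to 22.

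**Step 2: compare with the days named in SAP 3.2.**

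| Measure | Named days | Reached | Not reached | What else the SAP offers |
|---|---|---|---|---|
| EXACT total | 9, 16, 22 | 22 | 9, 16 | By-visit summary (4.11.3.3), no record defined |
| E-RS breathlessness | 9, 16, 22 | 22 | 9, 16 | By-visit summary (4.11.3.4), no record defined |
| E-RS cough | 9, 16, 22 | 22 | 9, 16 | Listing flag and the general descriptive sentence opening 4.11.3 |
| Cough NRS | 8, 15, 21 | 21 | 8, 15 | Visit-tied records (3.2.1.2.5) and by-visit summary (4.11.3.5) |

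There are 4 measures × 3 days = 12 values. The rule reaches 4 and misses 12 − 4 = 8. Of those 8, the 2 NRS values have named visit records. The other 8 − 2 = 6 (EXACT, E-RS breathlessness and E-RS cough at Days 9 and 16) have no selection rule anywhere.

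**Step 3: dose in the reachable window.** Protocol Table 3 shows 162 mg morning and evening on Days 17 to 21 and 162 mg in the morning of Day 22. No day in the window belongs to the 54 or 108 mg step.

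**Step 4: can the by-visit wording supply Days 9 and 16?** In Protocol Tables 1 and 2 the treatment visits are Day 8 (±1), Day 15 (±1) and Day 21. None is nominally on Day 9 or 16. Day 22 is a column without a visit number. A call made at the late edge of its window can fall on Day 9 or 16, but that is chance and not a rule.

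**Step 5: would the existing 5-day look-back work at the earlier days?** The look-back days are d − 5 to d − 1.

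- Day 9: Days 4 to 8. Table 3 has 27/27 mg on Day 4, 27 mg morning and 54 mg evening on Day 5, and 54/54 mg on Days 6 to 8. The window crosses a dose step.
- Day 16: Days 11 to 15, all 108/108 mg. The constant step begins on Day 10.
- Day 22: Days 17 to 21, all 162/162 mg.

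Only Day 9 would draw on an earlier step, and only if no entry from Days 6 to 9 exists. Lower limits of Days 6, 10 and 17 keep each look-back inside one step.

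**Step 6: evening entries on Days 9 and 16.** Table 3 gives 54 mg then 108 mg on Day 9, and 108 mg then 162 mg on Day 16. The diary is completed before bedtime, and the documents do not order it against the evening dose. A rule for these days therefore needs to say which step the entry is reported under.

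**Step 7: Visit 8.** The text of Protocol 6.3.2 gives Day 18; its heading, Table 2 and SAP 3.2.1.2.5 give Day 15. For subjects on active drug in Period 2, Table 3 has 108 mg on Day 15 and 162 mg on Day 18, so the two readings put the Visit 8 NRS at different dose steps.

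**The case against.** The strongest reply is that the SAP does not drop the earlier days. It keeps Days 9, 16 and 22 as endpoints, plans by-visit summaries for EXACT, breathlessness and the NRS, and lists all original and derived parameters (4.2.4). The same Day 22 sentence also appears under PROMIS (3.2.1.2.6), whose only scheduled post-baseline day in each period is Day 21. That suggests pasted text for the end-of-period record and not a decision to discard time points. The opening of 4.11.3 also promises descriptive summaries of secondary endpoints generally, which would take in E-RS cough.

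Much of this stands. A reader might infer that the trial will report no patient-reported result at 54 or 108 mg BID. The documents do not support that: the NRS has visit-tied Day 8 and 15 records and a by-visit summary, and EXACT and breathlessness have by-visit summaries planned. What the reply does not supply is a record for Days 9 and 16, or any specific summary or test of E-RS cough.

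A reader might also infer that one evening's score is itself an error and that means over constant-dose days should become the main value. That does not follow either. A single-day value is what the endpoint names, and windows such as Days 6–8, 10–15 and 17–21 contain none of the three named days. The gain in precision rests on an assumption: with k entries and day-to-day correlation ρ, the variance ratio to a single entry is (1 + (k − 1)ρ)/k. For k = 5 this is (1 + 4 × 0.5)/5 = 0.60 at ρ = 0.5 and (1 + 4 × 0.8)/5 = 0.84 at ρ = 0.8, and neither correlation comes from the documents. Replacing the main value would also be hard to defend after the unblinded interim look described in 4.11.1.5.

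**Conclusion.** The SAP contradicts itself on EXACT and E-RS. Its definitions assign one record at the 162 mg step, its endpoints name three days, and its by-visit summaries have no record defined for Days 9 and 16. Six of the nine EXACT and E-RS measure-by-day values lack a selection rule. E-RS cough is the clearest gap: 3.2.1.2.4 names it as a secondary endpoint alongside breathlessness, yet 4.11.3.4 plans the summary and t-test for breathlessness alone. For the NRS the fault is narrower: a pasted sentence that contradicts the instrument's own schedule and summary.

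This is more than missing detail, because the one rule that is stated cannot answer the escalating-dose objectives if applied literally. It should be corrected, but the reach is limited to secondary endpoints. The primary endpoint, sample size and alpha are untouched. The conclusion rests on day counts and on Table 3, not on any assumed correlation.

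**What to change.** - **3.2.1.2.3 and 3.2.1.2.4:** replace the Day 22 sentence with a rule that selects the evening diary record at each of Days 9, 16 and 22 in each period. If it is missing, take the last earlier entry, not before Days 6, 10 and 17 respectively, using the same days for placebo. State which dose step the Day 9 and Day 16 entries are reported under.
- **4.11.3.4:** add E-RS cough to the by-visit summary and the t-test. Here and in 4.11.3.3, name the day or days to which the t-test applies.
- **3.2.1.2.5:** remove the statements that the NRS is daily and that the Day 22 record is used; refer to the scheduled Day 8, 15 and 21 records.
- **Optional:** means over constant-dose windows may be added, as supportive results only.
- **Protocol 6.3.2:** reconcile Day 18 in the Visit 7 and 8 text with Day 15 in its heading and in Table 2.

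The cost is SAP wording and programming; no new data are needed. The blinded team should settle the rule before the general unblinding. If that date has passed, the clinical study report should say that the rule was fixed afterwards.

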3.2.1.2.5 Cough Severity Numerical Rating Scale

The Cough Severity Numerical Rating Scale instrument (Boulet et al 2015) is a single-dimension 11-point Likert scale ranging from zero ("no cough") to 10 ("worst possible cough").

A copy of the Cough Severity Numerical Rating Scale is provided in Protocol Appendix 2.

The scale will be administered on paper during the Screening Visit. Once a subject is randomized, the scale will be administered via the study specific e-diary in treatment period 1 at Visit 2 (Study baseline), Visit 3 (day 8), Visit 4 (day 15) and Visit 5 (day 21), in treatment period 2 at Visit 6(Baseline), Visit 7 (day 8), Visit 8 (day 15) and Visit 9 (day 21) and at premature discontinuation visit.

Questionnaire is recorded daily, the record collected on the Day 22 visit date will be used as the post baseline value in the summary tables; if a record is not available on the exact date then the last assessment prior to the Day 22 visit date, within a window of 5 days prior to the visit date, will be used. Study baseline value will be the last assessment available prior to the first IMP intake (as defined in this SAP at section 4.2.3).

3.2.1.2.6 PROMIS Item Bank v1.0 Fatigue Short Form 7a Scale

The PROMIS is a US National Institutes of Health (NIH) funded initiative to develop and validate PROs for clinical research and practice.

The PROMIS Fatigue Short Form 7a is a self-administered Likert-type rating 5-point scale of 7 questions that assess tiredness, exhaustion, energy, fatigue limit, tiredness to think, tiredness impact on hygiene and impact on ability to exercise strenuously over the past 7 days.

The PROMIS Fatigue Short Form 7a is provided in Protocol Appendix 3. This scale will be administered via the study specific e-diary during onsite visits (in treatment period 1 at Visit 2 (Study baseline) and Visit 5 (day 21), in treatment period 2 at Visit 6 (Baseline) and Visit 9 (day 21) and at premature discontinuation visit.

Questionnaire is recorded daily, the record collected on the Day 22 visit date will be used as the post baseline value in the summary tables; if a record is not available on the exact date then the last assessment prior to the Day 22 visit date, within a window of 5 days prior to the visit date, will be used. Study baseline value will be the last assessment available prior to the first IMP intake (as defined in this SAP at section 4.2.3).

3.2.1.2.7 Clinical Global Impression of Change Scale

The CGI-C provides an overall clinician-determined summary measure that takes into account all available information, including knowledge of the patient's history, psychosocial circumstances, symptoms, behavior, and the impact of the symptoms on the patient's ability to function.

The CGI-C is a one-item measure evaluating change from the initiation of treatment on a sevenpoint scale. The CGI-C can track clinical progress across time.

The CGI-C is provided in Protocol Appendix 5.

The CGI-C is collected in treatment period 1 at Visit 5 (day 21) and in treatment period 2 at Visit 9 (day 21).

3.2.2 Pharmacokinetic Variables

To determine the plasma concentration of nalbuphine and/or metabolites, blood samples will be collected at the Day 21 visits of each treatment period.

3.2.3 Safety Variables

3.2.3.1 Adverse Events

AEs will be recorded starting with the signing of the informed consent. All AEs will be collected through the follow-up visit of Treatment Period 2.

AEs definitions and analysis are reported in section 4.11.1 of this SAP.

3.2.3.2 Clinical Laboratory Tests

Clinical laboratory tests will be performed by a qualified central laboratory.

The following clinical laboratory analytes will be measured:

- Hematology: Hematocrit, hemoglobin, red blood cell count, white blood cell count, differentials (neutrophils, eosinophils, basophils, lymphocytes, and monocytes), platelet count, and reticulocytes
- Serum chemistry: Albumin, alkaline phosphatase, alanine aminotransferase, aspartate aminotransferase, blood urea nitrogen, calcium, chloride, carbon dioxide, creatinine, total

bilirubin, gamma-glutamyl transferase, glucose, lactic dehydrogenase, phosphorus, potassium, sodium, total cholesterol, total protein, and uric acid

- Urinalysis: Color, specific gravity, pH, glucose, ketones, protein, bilirubin, urobilinogen, blood, and microscopy (only on urine samples with abnormal urinalysis results)
- Coagulation: Prothrombin time, international normalized ratio, and activated partial thromboplastin time.

Clinical laboratory tests will be collected at Screening, in treatment period 1 at Visit 5 (day 21), in treatment period 2 at Visit 6 (Baseline) and Visit 9 (day 21) and at premature discontinuation visit.

